10.1.4 Action Taken

The investigator will describe the action taken with study drug in the appropriate section of the eCRF, as follows:

- None
- Study drug stopped
- Study drug temporarily interrupted
- Study dose modification
- Other, specify

10.1.5 Follow-up of Adverse Events

AEs are intended to be collected according to the procedures outlined above from the time of informed consent and to continue for 12 weeks following the last dose.

All investigators should follow up with patients with AEs until the event is resolved or until, in the opinion of the investigator, the event is stabilized or determined to be chronic. Details of AE resolution must be documented in the eCRF.

10.1.6 Documentation and Reporting of Adverse Events

AEs (including SAEs) should be reported and documented in accordance with the procedures outlined below. All AEs occurring during the study must be documented on the relevant eCRF pages. The following data should be documented for each AE:

- Diagnosed or description of the symptom if diagnosis is not established

-
- Classification of ‘serious’ or ‘not serious’
 - Severity
 - Date of first occurrence and date of resolution (if applicable)
 - Action taken with study drug
 - Causal relationship with study drug
 - Outcome of event (unknown, recovered, not yet recovered, recovered with sequelae, death [with date and cause reported])

10.2 Serious Adverse Events

10.2.1 Serious Adverse Events Definition

An SAE is any untoward medical occurrence or affect that, at any dose,

- Results in death
- Is life-threatening (an AE is life-threatening if the patient was at immediate risk of death from the event as it occurred, i.e., it does not include a reaction that might have caused death if it had occurred in a more serious form)
- Requires or prolongs inpatient hospitalization. (Complications occurring during hospitalization are AEs and are SAEs if they cause prolongation of the current hospitalization. Hospitalization for elective treatment of a pre-existing non-worsening condition is not, however, considered an AE. The details of such hospitalizations must be recorded on the medical history or physical examination page of the eCRF)
- Results in persistent or significant disability/incapacity. (An AE is incapacitating or disabling if it results in a substantial and/or permanent disruption of the patient’s ability to carry out normal life functions)
- Results in a congenital anomaly/birth defect

In addition, medical and scientific judgement is required to decide if prompt notification is required in situations other than those defined for SAEs above. This may include any event that the investigator regards as serious that did not strictly meet the criteria above but may have jeopardized the patient or required intervention to prevent one of the outcomes listed above, or that would suggest any significant hazard, contraindication, side effect, or precaution that may be associated with the use of the investigational product.

10.2.2 Serious Adverse Event Reporting and Documentation Requirements

Any SAE must be reported as detailed above (Documentation and Reporting of Adverse Events) by the investigator if it occurs from the time of signed consent through 30 days after the last dose of study drug (KZR-616), whether or not the SAE is considered to be related to the investigational product. After the reporting period, SAEs should be reported throughout the 12 week follow-up if the investigator assesses the event to be related to study drug. An SAE report consists of the SAE form, provided separately, along with requested additional source documentation as considered necessary.

SAEs that occur during the reporting period must be reported by the investigator to the Safety Reporting e-mail address, or dedicated fax (see below) and entered into electronic data capture (EDC) within 24 hours from the point in time when the investigator becomes aware of the SAE.

A copy of the SAE form should also be emailed or faxed **within 24 hours** for the attention of the study safety lead:

Contact Information:

SAE Reporting E-mail: [REDACTED]

Fax: [REDACTED]

The investigator should not wait to receive additional information to document fully the event before notification of a SAE, though additional information may be requested. Where applicable, information from relevant laboratory results, hospital case records, and autopsy reports should be obtained.

Instances of death, congenital abnormality, or an event that is of such clinical concern as to influence the overall assessment of safety, if brought to the attention of the investigator at any time after cessation of study drug administration and linked by the investigator to this study, should be reported to the study monitor.

The sponsor and/or the CRO will promptly notify all relevant investigators and the regulatory authorities of findings that could adversely affect the safety of patients, impact on the conduct of the study or alter the DMC/independent ethics committee (IEC)/institutional review board (IRB) approval/favorable opinion of the study. In addition, the CRO and the sponsor, will expedite the reporting to all concerned investigators, to the DMC/IRBs, where required, and to the regulatory authorities of all adverse reactions that are both serious and unexpected.

10.3 Pregnancy Reporting

Pregnancy occurring during a clinical investigation must be reported to safety within 24 hours on a Pregnancy Monitoring Form. The outcome of a pregnancy should be followed up carefully and any abnormal outcome of the mother or the child should be reported. This also applies to pregnancies following the administration of the investigational product to the father prior to sexual intercourse. Infants should be followed for a minimum of 8 weeks and all findings should be reported to the sponsor. Study drug is to be discontinued immediately.

If the outcome of the pregnancy meets a criterion for immediate classification as an SAE—spontaneous abortion (any congenital anomaly detected in an aborted fetus is to be documented), stillbirth, neonatal death, or congenital anomaly—the investigator should repeat the procedures for expedited reporting of SAEs as outlined above.

Full details will be recorded on the withdrawal page of the eCRF, or an SAE report will be completed if the patient has completed the study.

10.4 New or Worsening Disease Manifestations

New or worsening manifestation(s) of SLE should not be recorded as AEs unless they are assessed as serious.

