2.3.1 Proteasome Inhibitors for the Treatment of Inflammatory Disorders

The proteasome has been posited as a target for drug development in chronic inflammatory conditions and autoimmune disorders.²⁹ Bortezomib blocks cytokine release from immune effector cells and has demonstrated anti-inflammatory activity in several animal models of autoimmune disorders including rheumatoid arthritis (RA)³⁰ and SLE³¹. More recently, bortezomib was shown to have rapid clinical activity in patients with refractory SLE and LN who had failed standard immunosuppressive therapies^{32, 33, 34}. However, systemic toxicities associated with dual-targeting proteasome inhibition, such as anemia and thrombocytopenia, restrict chronic administration³⁵. Further, bortezomib is associated with a dose-limiting side effect of peripheral neuropathy, likely caused by off-target inhibition of the serine protease HtrA2 in neurons³⁶. Peripheral neuropathy is not induced by peptide ketoepoxide proteasome inhibitors such as carfilzomib^{36, 37}.

The discovery of PR-957 (now called ONX 0914), a selective immunoproteasome inhibitor, demonstrated that the immunomodulatory and anti-inflammatory effects of dual-targeting proteasome inhibitors are due to inhibition of immunoproteasome activity in immune effector cells and inflamed tissues^{38, 39}. ONX 0914 is a tripeptide ketoepoxide analog of carfilzomib that selectively inhibits the immunoproteasome in vitro and upon administration to mice.

ONX 0914 exposure inhibited cytokine production in immune effector cells, reduced the number and activity of inflammatory T-cell subsets such as T helper (Th)1 and Th17, increased the number of regulatory T cells, and blocked autoantibody formation^{38,39,40}. ONX 0914 was shown to be therapeutically active in mouse models of SLE, in which it demonstrated equivalent activity but better tolerability than bortezomib^{38,41}. In addition, treatment of mice with ONX 0914 did not reduce the number of splenic lymphocytes or impair viral clearance in multiple infection models^{39,41}.

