4.1.1.1 Dose-Limiting Toxicities

A DLT is defined as any Grade 3 or higher study drug-related AE, according to National Cancer Institute Common Terminology Criteria for Adverse Events (NCI-CTCAE), Version 4.03, that occurs during the 4-week DLT evaluation period, with the following exceptions:

- Asymptomatic Grade 3 anemia, neutropenia, or thrombocytopenia returning to baseline or Grade ≤ 2 within 7 days without transfusion, growth factor support, or other active therapeutic intervention
- Grade 3 study drug administration-related reactions (e.g., systemic drug reaction), fatigue, anorexia, chills, nausea, diarrhea or vomiting lasting < 1 day

-
- Asymptomatic, isolated Grade 3 or higher changes in alkaline phosphatase, creatine phosphokinase, gamma-glutamyl transferase, lipase, or lymphocyte count

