5.2 Inclusion and Exclusion Criteria

5.2.1 Inclusion Phase 1b

1. Male or female patients aged 18 to 75 years (inclusive)
2. Body mass index (BMI) of 18 to 40 kg/m²
3. Fulfills the 2012 SLICC classification criteria for SLE
4. Have at least one of the following at screening per central lab:
 - a) Positive ANA test (1:80 or higher); or
 - b) Anti-dsDNA antibodies elevated to above normal (i.e., positive results); or
 - c) Anti-Smith antibody elevated to above normal (i.e., positive results)
5. Active SLE as indicated by a SLEDAI-2K total score ≥ 4 at screening
6. Must have received 1 or more of the following therapies for SLE, each administered at or higher than the minimum dose indicated for at least 12 weeks (unless discontinued or dose adjusted for documented drug-related toxicity or size/weight):
 - a) Hydroxychloroquine 200 mg orally daily in combination with prednisone 10 mg daily or equivalent
 - b) MMF orally 1 g/day or MPA orally 720 mg/day
 - c) Methotrexate orally or SC 15 mg/wk., or leflunomide orally 10 mg/day

-
- d) AZA 100 mg/day or 6-mercaptopurine 50 mg/day (50 or 25 mg/day, respectively, permitted in cases of documented thiopurine methyltransferase [TPMT] polymorphism) orally
 - e) Cyclosporine or tacrolimus at doses documented to maintain at least 100 or 5 ng/mL during the required duration, respectively
 - f) Cyclophosphamide 500 mg IV every 2 weeks or 500 mg/m² IV once monthly
 - g) Belimumab 10 mg/kg IV every 2 weeks for 3 doses, followed by 10 mg/kg every 4 weeks; or 200 mg SC weekly
 - h) Rituximab 1 g IV (may be given as 500 mg twice)
7. Acceptable screening laboratory values of concern, including:
- a) Adequate hematologic criteria:
 - Absolute neutrophil count $\geq 1.5 \times 10^9/L$ ($\geq 1 \times 10^9/L$ if neutropenia is attributable to lupus disease activity)
 - White blood cells $\geq 2.0 \times 10^9/L$ ($\geq 1.5 \times 10^9/L$ if leukopenia is attributable to lupus disease activity)
 - Hemoglobin (Hgb) ≥ 9 g/dL (≥ 8 g/dL if anemia is attributable to lupus disease activity)
 - Platelet count $\geq 100 \times 10^9/L$ ($\geq 25 \times 10^9/L$ if thrombocytopenia is attributable to lupus disease activity)
 - b) Adequate hepatic function:
 - Total bilirubin $\leq 1.5 \times$ upper limit of normal (ULN) ($3 \times$ ULN for patients with documented Gilbert's syndrome)
 - Aspartate aminotransferase (AST) $\leq 2.5 \times$ ULN
 - Alanine aminotransferase (ALT) $\leq 2.5 \times$ ULN

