9 STUDY DISCONTINUATION

9.1 Individual and Study Stopping Rules for Safety (Phase 1b/2)

Study Stopping Rules

If any of the following events occur, administration of study drug will be temporarily discontinued until a thorough review of the accumulated safety data is undertaken by the DMC.

- Death in any patient, unless the cause of death is due to obvious alternative etiology
- Unexpected life-threatening event in any patient, unless due to obvious alternative etiology.
- Three (3) or more of the same Grade 3 or higher AE (judged by the investigator, medical monitor, or sponsor's representative), including injection site reactions, occurring in 20% or more individuals in any dose group, unless due to obvious alternative etiology
- Any event which, in the opinion of the investigator, medical monitor, DMC or sponsor's representative, contraindicates further dosing of additional patients

Individual Patient Stopping Rules

If any of the following events occur, administration of study drug to an individual patient should be discontinued until a review of the accumulated safety data is undertaken by the DMC.

- Any event which fulfills criteria for DLT, within or outside the DLT (see [Section 4.1.1.1](#)) in Phase 1b or Phase 2, evaluation period
- Any unexpected SAE, unless due to obvious alternative etiology
- Any event which fulfills criteria for a Study Stopping Rule, including any life-threatening or SAE, unless due to obvious alternative etiology
- Any event which, in the opinion of the investigator, medical monitor, DMC or sponsor's representative, contraindicates further dosing

After such a review, resumption of dosing may be considered at the same or lower dose including consideration for any prophylactic interventions (e.g. as per [Section 7.1.3](#)).

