10 ADVERSE EVENTS AND SERIOUS ADVERSE EVENTS

10.1 Adverse Event Reporting

10.1.1 Definitions

An AE is defined as any untoward medical occurrence in a clinical study patient administered a medicinal product, which does not necessarily have a causal relationship with this treatment. An AE can therefore be any unfavorable and unintended sign (including an abnormal laboratory finding), symptom, or disease temporally associated with the use of a medicinal (investigational) product, whether or not it is related to the medicinal (investigational) product. This includes an exacerbation of pre-existing conditions or events, intercurrent illnesses, drug interaction or the significant worsening of the indication under investigation that is not recorded elsewhere in the eCRF under specific efficacy assessments. Anticipated fluctuations of pre-existing conditions, including the disease under study, that do not represent a clinically significant exacerbation or worsening need not be considered AEs.

It is the responsibility of the investigator to document all AEs that occur during the study. AEs will be elicited by asking the patient a nonleading question, for example, "Have you experienced any new or changed symptoms since we last asked/since your last visit?" AEs should be reported on the appropriate page of the eCRF.

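### Section 10.4 keeps non-serious SLE manifestations of any grade off the AE record, out of step with 10.1.1 and 9.3, so ambiguous Grade 3 or higher events can miss causality, DLT and stopping-rule review

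*Combined protocol and SAP*

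**What the plan says.** Section 10.4 is a single sentence: "New or worsening manifestation(s) of SLE should not be recorded as AEs unless they are assessed as serious". Seriousness is the only way in.

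Section 10.1.1 defines an AE to include abnormal laboratory findings, whether or not related to the drug. It also includes "the significant worsening of the indication under investigation that is not recorded elsewhere in the eCRF under specific efficacy assessments". Expected ups and downs in an existing condition, lupus included, are exempt only if they are ones "that do not represent a clinically significant exacerbation or worsening need not be considered AEs".

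Two sections deal with physical examination. Section 8.2.3 follows 10.4: lupus signs already scored in the disease instruments are not recorded at the brief examination unless they are SAEs. Section 9.3, for the Early Withdrawal Visit, has every examination change from baseline entered as an AE, with no lupus exception.

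The decision rules are worded in AEs:

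- Section 4.1.1.1: "A DLT is defined as any Grade 3 or higher study drug-related AE", with listed exceptions.
- Section 9.1, study stopping: "Three (3) or more of the same Grade 3 or higher AE", in at least 20% of a dose group, unless another cause is obvious.
- Section 7.1.1: alongside laboratory thresholds, a pre-dose criterion on the grade of AEs other than injection site reactions.
- Section 10.1.3: AEs are taken as related unless clearly not.

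The Phase 2 safety endpoint (11.1.2) and the synopsis version of the Phase 1b primary endpoint rest on AEs alone. The Phase 1b endpoint in 11.1.1 also includes safety laboratory findings.

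**The concern.** The findings that lupus produces overlap with those that the safety system is meant to detect. Section 2.1.1 lists hemolytic anemia, thrombocytopenia and glomerulonephritis among the manifestations of SLE. Section 2.3.1 says that "systemic toxicities associated with dual-targeting proteasome inhibition, such as anemia and thrombocytopenia, restrict chronic administration". Section 10.5.2 gives hemolytic anemia, thrombocytopenia and renal failure as presenting features of TMA. Patients may enter with platelets as low as 25 x 10^9/L "if thrombocytopenia is attributable to lupus disease activity" (5.2.1, and likewise 5.2.3 for Phase 2).

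A site that sees a non-serious Grade 3 platelet fall must therefore decide whether it is lupus before deciding whether it is an AE. If the answer is lupus, 10.4 leaves no AE to grade, assess for causality or count. Both phases are open-label without a control arm, so no comparison group can later show whether events filed as lupus were more frequent than expected. Safety is the primary objective of Phase 1b and a secondary objective of Phase 2.

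**Working it through.** **1. The sections side by side, for a non-serious Grade 3 or higher event attributed to SLE**

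| Event | 10.1.1 | 10.4 |
|---|---|---|
| Clinically significant worsening, not captured as efficacy data | AE | Not recorded |
| Abnormal laboratory finding, clinically significant | Within the AE definition | Not recorded if called an SLE manifestation |
| Worsening recorded under efficacy assessments | Exempt from the worsening clause | Not recorded |
| Fluctuation that is not clinically significant | Exempt | Not recorded |

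The mismatch is in the first two rows. In the third row the sections agree, but information is still lost. By 8.2.6.11, SLEDAI-2K weights which manifestation is present, not how severe it is, and BILAG is used only in Phase 1b. Neither score supplies a CTCAE grade or a causality judgement. Separately, 9.3 conflicts with 8.2.3 and 10.4 on examination findings.

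**2. Were such events meant to be judged?** The cytopenia exception in 4.1.1.1 covers asymptomatic Grade 3 anemia, neutropenia or thrombocytopenia that recovers within 7 days without intervention. A further exception covers isolated, asymptomatic lymphocyte changes. Other drug-related Grade 3 or higher cytopenias were therefore meant to count. The stopping rule in 9.1 has its own exit for an obvious alternative cause. Clear disease events can thus leave inside the safety review; 10.4 also removes the unclear ones, and does so earlier.

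**3. The plan's own percentages (4.1.1.2), reproduced**

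- Escalate: 0/4 = 0%, 1/6 = 16.7%, 1/5 = 20%, all at or below the stated 20%.
- Do not escalate: 1/4 = 25% as stated, 2/6 = 33.3%, 2/5 = 40%.

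**4. Effect of one unrecorded event that would otherwise have qualified**

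- Six evaluable patients: 2/6 = 33.3% (stop) becomes 1/6 = 16.7% (go).
- Five: 2/5 = 40% (stop) becomes 1/5 = 20% (go).
- Four: 1/4 = 25% (stop) becomes 0/4 = 0% (go).
- Phase 2 stopping rule: 0.20 x 20 = 4 patients. 4/20 = 20% (met) becomes 3/20 = 15% (not met). This takes all 20 patients as the denominator and counts each patient once.

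**5. Illustration over a range.** The documents give neither the true rate p of qualifying events nor the share f of them filed as SLE, so both are assumed. With patients independent, the recorded rate is q = p(1 - f).

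Chance of escalating with n = 6: P(X <= 1) = (1 - q)^6 + 6q(1 - q)^5. For p = 0.30, f = 0: 0.1176 + 0.3025 = 0.420.

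| p | f = 0 | f = 0.25 | f = 0.50 |
|---|---|---|---|
| 20% | 65.5% | 77.6% | 88.6% |
| 30% | 42.0% | 59.4% | 77.6% |
| 40% | 23.3% | 42.0% | 65.5% |

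Chance that the Phase 2 rule is met with n = 20: P(X >= 4).

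| p | f = 0 | f = 0.25 | f = 0.50 |
|---|---|---|---|
| 10% | 13.3% | 5.8% | 1.6% |
| 20% | 58.9% | 35.2% | 13.3% |
| 30% | 89.3% | 69.0% | 35.2% |

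These tables show how sensitive the rules are to under-recording. They do not estimate how much there will be.

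**The case against.** The strongest reply is that 10.4 removes little that would have counted. A DLT must be drug-related, and the table in 10.1.3 reserves that label for events that concurrent disease cannot explain. The three-event rule already excuses an obvious alternative cause. An event that a site confidently calls lupus would often fail both tests even if recorded. This stands, and it limits the size of the problem. It does not remove it: 10.1.3 also presumes relatedness unless an event is clearly unrelated, so ambiguous events could count, but only once they are on the AE page.

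The second reply is that other safeguards remain:

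- Laboratory data are part of the safety evaluation in both phases (11.2.1, 11.3.1).
- TMA is an AE of special interest, reportable within 24 hours, and suspicion of it interrupts dosing (10.5, 10.5.2).
- The hematologic and hepatic criteria in 7.1.1 act on laboratory values.
- The 9.1 catch-all needs no AE record.
- The DMC reviews safety data generally (10.7).

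All of this is true, but the cover is partial. Descriptive laboratory summaries do not feed AE-worded counts, the catch-all depends on someone's opinion, and 7.1.1 lists no renal laboratory value.

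A reader might infer that these events vanish from the safety endpoint altogether. The Phase 1b endpoint in 11.1.1 does not support that, because it includes laboratory findings. A reader might also infer that 10.1.1 flatly contradicts 10.4. It does not: its worsening clause has its own exemption for what is recorded as efficacy data.

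**Conclusion.** The point holds as a conflict between sections with a possible downward bias in AE counts. The bias is confined to events that are called SLE, are not serious and are Grade 3 or higher. Those events are absent from the AE tables, the Phase 2 safety endpoint, and the DLT and three-event counts.

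One event is enough to reverse a cohort decision or keep the Phase 2 rule from being met. This requires that the event would otherwise have been judged drug-related (DLT), or to have no obvious alternative cause (stopping rule). The documents give no basis for how often that would occur.

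It would go too far to say that the plan hides known toxicities of KZR-616. Section 2.3.1 attributes anemia and thrombocytopenia to the dual-targeting inhibitors. Section 2.4 reports that KZR-616 appeared not to cause persistent abnormalities of that kind after 4 weeks, and 2.5.1 describes occasional, typically transient Grade 1 changes in healthy volunteers. The concern is that the recording rule weakens the trial's ability to confirm this in patients.

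The supplied text contains neither the separate SAP, which takes precedence under 11.3.1, nor the DMC charter. Either may address these events, but neither can recover a grade or causality judgement that was never collected.

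**What to change.** Reconcile 10.4 with 10.1.1, 8.2.3 and 9.3. The reconciled text should have clinically significant SLE manifestations of Grade 3 or higher recorded as AEs, with an SLE-manifestation flag, a CTCAE grade and a causality assessment. It should say plainly that scoring such an event in a disease instrument does not replace the AE record. Tabulate AEs with and without the flagged events, so that disease activity stays separable from the rest.

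The requirement should not extend to every hematologic or renal laboratory worsening. That would contradict the 10.1.1 exemption for fluctuations that are not clinically significant and, in a nephritis population, would fill the AE tables with routine variation.

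How flagged events are handled under 4.1.1.1, 7.1.1 and 9.1 is for the sponsor to reconcile and state; recording an event does not by itself make it a DLT.

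The cost is protocol wording, eCRF guidance, one extra table and a somewhat higher reported AE incidence. No visits, tests or patients are added.
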